1 OBJECTIVES

1. To prospectively randomize patients to one of two fractionation regimens of whole breast radiotherapy with a concomitant boost as part of breast conservation therapy in post-menopausal women with T1-2 N0 breast cancers or Stage 0 (Tis) DCIS: 4050 cGy whole breast radiotherapy with a concomitant tumor bed boost to 4800 cGy to the tumor bed in 15 fractions (Arm 1) versus 3200cGy whole breast radiotherapy with a concomitant tumor bed boost to 4200 cGy in 10 fractions (Arm 2).
2. To assess the rate of acute toxicity (grade 3 or higher).
3. To assess the rate of long-term fibrosis (grade 3 or higher) and changes in breast cosmesis in the 2 arms at 2-3 years and at 5 years.
4. To assess and compare local control at 2-3 years and at 5 years between the two arms.

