1.1 Study Hypothesis

A hypo-fractionation breast radiotherapy regimen delivered over two weeks is not inferior to standard treatment over three weeks (whole breast radiotherapy with a concomitant boost), in terms of acute toxicity and long term fibrosis, breast cosmesis and local control, at 2-3 years and at 5 years follow up.

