where α / β is a tissue dependent parameter, arising from the radiobiological linear - quadratic cell survival model.

From the randomized prospective trials, there is an estimate that breast cancer may have an alpha/beta for tumor control of 4.6 and normal breast tissue an alpha beta ratio of 3.4 [6]. The relative closeness in alpha/beta ratios of tumor and normal tissue would support a rationale for hypo-fractionation [20-23]. Based on the formula above, Table 1 includes the calculation of BEDs (biologically equivalent doses) between the 2 arms. The breast cavity is predicted to have an alfa/beta value between 3-4.

Based on Table 1 a regimen of 42 Gy in 10 fraction to the boost is comparable to 48 Gy in 15 fractions. The latter regimen has been proven to both be effective (local recurrence rate <5% at 5 years) and to be associated with excellent cosmetic results (16), justifying our choice for a biologically equivalent regimen) in the experimental arm comparable to standard arm (see α/β values in Table 1, in bold).

In view of the fact that most recurrences tend to occur at the original tumor bed and that other studies have shown efficacy of lower doses of adjuvant radiation to the rest of the breast (4-8), we elect to test a dose of 32 Gy in 10 fractions. Maintaining a relative low dose to the rest of the breast tissue, which is a much lower risk of local recurrence than the area of the tumor cavity, will reflect on very low risk of fibrosis and will enhance the likelihood of optimal breast symmetry and cosmesis.

TABLE 1

Alfa/Beta (Gy)	2 Gy x 23	2.7 Gy x 15	3.2 Gy x 15*	3.2 Gy x 10	4.2 Gy x 10*
2	46	47	62.4	41.6	65.1
3	46	46.1	59.5	39.68	60.48
4	46	45.2	57.6	38.4	57.34
10	46	42.8	52.8	35.2	49.7

- Boost Dose delivered at tumor bed

3 Staging Criteria

TNM Stage 0 (Tis N0 M0), Stage I-II, T1-2 N0 M0, newly diagnosed breast cancer patients.

4 Patient Eligibility

Inclusion criteria:

1. Women status post segmental mastectomy
2. If unilateral, pT1-2 breast cancer excised with negative margins
3. If bilateral, pT1-2 breast cancer excised with negative margins AND/OR pTis excised with negative margins.
4. Clinically N0 or pN0 or sentinel node negative
5. Ductal carcinoma in situ DCIS with negative margins (no DCIS on inked margins).
6. Women with previous contralateral breast cancer.

Exclusion criteria:

1. Previous radiation therapy to the ipsilateral breast.
2. 90 days from last surgery, unless s/p adjuvant chemotherapy

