9 STUDY CALENDAR

All patients will be followed a month after the completion of treatment. Our routine follow up is once a year after completion of radiation therapy. **For the purpose of protocol significance (for assessment of fibrosis), we will require at least one follow up in the department visit after the**

second year. Acute and late effects will be recorded following the criteria described in Appendix 1. At each post treatment follow-up visit, a physical exam to detect clinical recurrence will be performed. Mammographic studies and/or MRI will be performed and reviewed on an annual basis.

The degree of fibrosis assessed by palpation will be measured as per Appendix 1, late effects at 2-3 years and at 5 years. Local control at 2-3 years and at 5 years will be extracted from the medical record, and can be derived from clinical reports from medical, surgical or radiation oncologists as well as from the primary care doctor who is following the patient.

Table 4: Study Calendar

Study	Pre Entry	Weekly[‡]	Post Treatment Follow-up visits
Mammogram	X		X**
Lumpectomy pathology report	X		
Medical History	X		X*
BCTOS and quality of life surveys[⊕]	X		X
Physical exam	X	X	X*
Consent Form	X		
Randomization	X		
Treatment simulation	X		
Weekly CBCT prior to RT treatment		X	
Port films/ each RT dose after the first one		X	
Skin Assessment	X	X	X*

[‡] - performed weekly during the weeks of radiation therapy.

* Our routine follow up is once a year after completion of radiation therapy. For the purpose of protocol significance (for assessment of fibrosis), we will require at least one follow up visit after the second year.

** Standard annual mammogram (or MRI) for both breasts will be accepted as follow up data.

⊕ Quality of life surveys will be sent to the patients' personal email address. Completed responses will be sent directly to our REDCAP database. The quality of life survey completion is optional. The receipt of the BCTOS survey will be recorded by the research nurses assigned to the study, but completion is not mandatory. The BCTOS and quality of life questionnaires will administer before treatment (baseline), at the end of RT, at 1-month follow up visit and at 2-year follow up visit.

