10 CRITERIA FOR EVALUATION AND ENDPOINT DEFINITIONS

- Acute and late toxicity will be reported as scheduled in the above study calendar (10.1) following the criteria in Appendix 1.
- Local recurrence will be classified as it follows:
- Local recurrence within the field of conformal radiation is defined as TRUE LOCAL RECURRENCE.
- Axillary/ intra-mammary or supraclavicular recurrence in the same side of the index lesion will be defined as REGIONAL RECURRENCE /SAME BREAST.
- At the time of local recurrence all patients will undergo disease assessment with CT of Chest/ Abdomen/ Pelvis and, if symptomatic, bone scan and/or brain MRI.
- Local/regional recurrences will be further grouped as:
- ISOLATED LOCAL/REGIONAL RECURRENCES
- CONCOMITANT LOCAL/REGIONAL AND DISTANT RECURRENCES

Patients developing local recurrences after systemic recurrence has been documented will be classified as:

- METACRONOUS LOCAL/REGIONAL RECURRENCES.
- CONTRALATERAL BREAST CANCER will also be recorded and reported as invasive and noninvasive.

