To summarize the safety data, distributions of toxicity grades will be provided by treatment arm. Noninferiority tests will be conducted to test the primary hypothesis that the 2 weeks regimen would result in no more toxicity than did the 3 weeks regimen. Fisher exact tests will be used to compare the distributions of acute and late toxicity grades between the 2 weeks arm and the 3 weeks arm.

The comparison of the cumulative incidence of long term fibrosis or telangiectasia grade ≥ 2 between the 2 arms will be conducted using log-rank χ^2 tests. The hazard ratio between the 2 arms will be computed with the 95% confidence intervals.

Local recurrence-free survival will be estimated for both treatment arms using Kaplan-Meier curves, the relative risk will be estimated, and the 2 arms will be compared using the log-rank χ^2 tests.

11.1 Data management:

Data Management will be carried out by staff of the Department of Radiation Oncology at WCMC under the direction of [name]. Randomization will occur from a randomization list provided by [name]'s team and allocation to each arm will be performed, after consent is acquired, by the research team in the department of Radiation Oncology. The Randomization will be a manual process where the data manager will enter the consented patient's name in a sequential order in the Randomization list provided. Data will be entered into the JCTO Clinical database management system maintained by the JCTO according to the procedures of WCM. Patients will be followed every 12 months to evaluate their status with respect to recurrence. Recurrences will be evaluated using standard criteria in the Dept. of Radiation Oncology that are provided in the protocol. Data will be transferred from the Clinical database to the Division of Biostatistics for analysis. The Principal Investigator, Research Nurse and Data Manager have access to data collected.

Analysis: Patient characteristics at randomization will be summarized by treatment group using descriptive statistics and graphical displays.

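### Local control is analysed as local recurrence-free survival with no rule for deaths; read literally, deaths count as events and would dilute a difference in local control

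*Combined protocol and SAP*

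**What the plan says.** Objective 4 in Section 1 is "To assess and compare local control at 2-3 years and at 5 years between the two arms". Section 1.1 includes local control among the outcomes on which the two-week regimen "is not inferior to standard treatment over three weeks", and the Protocol Summary lists it as a secondary endpoint.

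The only analysis given for it is in Section 11: "Local recurrence-free survival will be estimated for both treatment arms using Kaplan-Meier curves", after which "the relative risk will be estimated, and the 2 arms will be compared using the log-rank" chi-square test. No margin, alpha, power or event count is attached to this comparison.

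The event is not defined there. Section 10 classifies recurrences (for example, "Local recurrence within the field of conformal radiation is defined as TRUE LOCAL RECURRENCE") and does not mention death. Section 9 says "Local control at 2-3 years and at 5 years will be extracted from the medical record", and Section 11.1 adds "Patients will be followed every 12 months to evaluate their status with respect to recurrence". Section 2.3 gives the benchmark for the 15-fraction regimen: "local recurrence rate <5% at 5 years".

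**The concern.** Survival free of local recurrence, in its ordinary sense, means being alive without local recurrence. An analyst who applied Section 11 literally would count deaths from any cause and would be testing recurrence or death, which is not objective 4. An analyst who worked from Section 10 and the follow-up text would count recurrences only. Both could claim to follow the plan, and the choice could be made after the data are seen.

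The literal reading errs in an unhelpful direction. Deaths unrelated to the fractionation schedule add about the same number of events to each arm and move the hazard ratio towards 1. The trial hopes to conclude that local control is not inferior, and Table 1 in Section 2.3 shows a lower whole-breast equivalent dose in Arm 2 (38.4 against 45.2 at an alpha/beta of 4). A diluted comparison could hide a loss of local control. The 5-year figure would also not be a local recurrence rate, so it could not be set beside the benchmark in Section 2.3.

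**Working it through.** The plan gives no figure of its own for local control, so there is none to reproduce. The check asks how much the choice of event matters.

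**Inputs from the documents.** 200 patients per arm (Protocol Summary); local recurrence below 5% at 5 years on the standard regimen (Section 2.3), with 5% taken as the upper bound.

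**Assumptions.** 5-year mortality of 2%, 5% or 10%, equal in both arms (the documents give none); true local-recurrence hazard ratio 2.0; constant hazards; 5 years of complete follow-up; two-sided 0.05.

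**Step 1: hazards per year.** λ = −ln(1 − p)/5.
- Recurrence, control arm: −ln(0.95)/5 = 0.01026.
- Death: 0.00404 (2%), 0.01026 (5%), 0.02107 (10%).

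**Step 2: hazard ratio when deaths count.** HR_c = (HR × λ_LR + λ_D)/(λ_LR + λ_D).
- 2% mortality: (0.02052 + 0.00404)/(0.01026 + 0.00404) = 1.72.
- 5% mortality: (0.02052 + 0.01026)/(0.01026 + 0.01026) = 1.50.
- 10% mortality: (0.02052 + 0.02107)/(0.01026 + 0.02107) = 1.33.

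**Step 3: power.** Schoenfeld: Φ(√E × ln(HR)/2 − 1.96), where E is the expected number of events.

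| 5-year mortality | Recurrences | Power, recurrence only | Recurrences or deaths | HR, deaths counted | Power, deaths counted |
|---|---|---|---|---|---|
| 2% | 29.2 | 46% | 36.9 | 1.72 | 38% |
| 5% | 28.8 | 46% | 48.0 | 1.50 | 29% |
| 10% | 28.0 | 45% | 66.6 | 1.33 | 21% |

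For the 5% row: √48.0 × ln(1.50)/2 − 1.96 = −0.56, and Φ(−0.56) = 0.29. A log-rank simulation of that row (4,000 runs) gave 45% for recurrence only and 29% with deaths counted. Under no effect, simulated size stayed at about 5% for both definitions, so the harm is lost sensitivity and not false findings of a difference.

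**Step 4: a larger effect.** With recurrence of 3% against 9%, the hazard ratio is ln(0.91)/ln(0.97) = 3.1. With 5% mortality it becomes 1.8 when deaths count, and simulated power falls from about 72% to 46%.

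**Step 5: the reported rate.** If deaths count, the control-arm 5-year event rate is 1 − 0.95 × 0.98 = 6.9%, 1 − 0.95 × 0.95 = 9.8%, or 1 − 0.95 × 0.90 = 14.5%. None of these can be compared with a recurrence rate below 5%.

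**Step 6: if deaths are censored instead.** The log-rank test then compares the cause-specific hazard of local recurrence, and Step 2 does not apply. One minus Kaplan-Meier gives 5.0% in the control arm; the cumulative incidence with death competing is 4.9% at 5% mortality and 4.7% at 10%. The standard error of a 5% rate in 200 patients is √(0.05 × 0.95/200) = 1.5 points, so this bias is minor.

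**Step 7: what neither definition cures.** 80% power at a hazard ratio of 2.0 needs 66 events (Schoenfeld). About 28 to 30 recurrences are expected.

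**The case against.** The strongest reply is that the plan never says deaths are events. Section 10 names only recurrences, the annual follow-up is for recurrence status, and the Protocol Summary speaks of a local control rate. The absence of death from these sections can be read as evidence that only recurrence was meant. The contrast with fibrosis, which Section 11 describes as a cumulative incidence, does not settle the matter, because that endpoint is also compared by log-rank test with no competing-risk method named. This stands. A reader might infer that the plan definitely tests recurrence or death; the documents do not support that, because it rests on the usual meaning of a label that no section defines.

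It also stands that the losses above need three conditions: deaths counted, an assumed mortality, and a sizeable true hazard ratio. Nothing in the documents shows that deaths would equal or outnumber recurrences.

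A reader might further infer that the analysis is biased in favour of the experimental arm. That goes too far. Dilution helps Arm 2 only if a non-significant test of difference is taken as proof of non-inferiority, and Section 11 prescribes non-inferiority testing for toxicity only. The missing margin is a separate gap.

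What the reply does not remove is that the variable named in Section 11, applied as written, answers a different question from objective 4, and that no section directs the analyst otherwise.

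**Conclusion.** The point holds in a limited form. The label in Section 11 does not match the objective, and the handling of deaths is unstated. On the literal reading, with 5% control recurrence and a true hazard ratio of 2.0, the loss is about 8, 17 or 24 points of power at 2%, 5% or 10% assumed mortality, and the reported rate is no longer one of local recurrence. With deaths censored, almost all of this disappears. The sizes depend on assumed mortality balanced between arms, constant hazards and complete follow-up. Local control is a secondary endpoint without its own power or alpha, so this is a worthwhile and cheap correction, not a threat to the trial's primary conclusion.

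**What to change.** In Section 11, replace local recurrence-free survival with time to ipsilateral local recurrence, and treat death without local recurrence as a competing event. State which Section 10 categories count, and how regional, distant and contralateral events are handled. Report:
- cumulative incidence (Aalen-Johansen) by arm with 95% confidence intervals at 2-3 and 5 years;
- the cause-specific log-rank test and hazard ratio with 95% confidence interval;
- recurrence or death as a supplementary summary.

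The cost is a wording change in the plan and a few lines of code. Date of death must be captured through year 5; it is needed for censoring in any case. The drawback is fewer events than a composite would have, and so a wider interval.

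This change does not supply a non-inferiority margin or raise power. The plan should either pre-specify a margin for local control or call the comparison descriptive, and should say that a non-significant log-rank result is not evidence of non-inferiority.

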12 REGISTRATION GUIDELINES

At the time of registration, informed consent form must be signed by the patient, and the treating physician obtaining the consent. The Consent is then scanned to the patient's chart in EPIC and a scanned copy is sent to the Rad.Onc Clinical Trials office for patient registration. Please email [contact] the scanned informed consent and the completed eligibility document.

- At the time of registration, the eligibility registration worksheet will be completed. A complete Eligibility document will be required before randomization can occur.
- Patients will be registered in the Department of Radiation Oncology enrollment log in

REDCAP and in the JCTO oncore system. Registration confirmation emails will be sent out by the CancerCTRegistrar after the consent and eligibility is reviewed by the Cancer CT registration team from JCTO. Any questions or concerns regarding registration should be directed to [contact].

ROCTO will also send out an enrollment notification email to all radiation oncology personnel involved in the study including the billing team.

- Patient will be marked as “Research” in ARIA and subsequently the protocol specific Pre-CRFS will be populated for the patient in the clinical trial database in REDCAP.

12.1 Confidentiality

All data and medical information obtained once a patient has decided to participate in this research, will be kept confidential to the extent permitted by law and will not be released without the patient’s written permission except as described in this paragraph. In all study forms, patients will be identified only by their initials and patient number. Patient names will not be reported in any publication; only the data obtained as a result of their participation in this study will be made public.

12.2 Registration information for sub-sites:

Once the patient is consented, the sub-site should email the WCMC radiation oncology research team at [contact] the following documents within 24 hours :

- 1 Eligibility checklist/randomization
- 2 Enrollment form -sent via email
- 3 Online enrollment form (via REDCAP) when ready

WCMC research study team will assign a trial ID number and randomize patients to one of the 2 arms of the study. Since this is a randomized study, we request that the sites notify WCMC immediately.

13 Adverse Event Reporting and Medical Monitor

Adverse events (AEs) will be recorded in the case report form for the duration of the trial, regardless of whether or not the event(s) are considered related to the trial. All AEs considered related to study intervention will be followed until resolution even if this occurs post-trial.

13.1 Reporting adverse events

13.1.1 Adverse events

Adverse events will be recorded for the duration of a patient’s participation in the trial. All adverse events (except grade 1 and 2 laboratory abnormalities unless a dose treatment modification, delay or therapeutic intervention is required), regardless of causal relationship, are to be recorded in the case report form and source documentation. Pre-existing conditions at baseline will be recorded. If a pre-existing condition does not change, it does not have to be reported on subsequent cycles.

The investigator must determine the toxicity of adverse events according to the CTCAE version 5.0 (Appendix 1) and their causal relationship.

13.1.2 Assessing and Recording Adverse Events

An adverse event is defined as any untoward medical occurrence in a patient or clinical investigation participant administered a pharmaceutical product and which does not necessarily have to have a causal relationship with this treatment. An adverse event can therefore be any unfavorable and unintended sign (including an abnormal laboratory finding, for example), symptom, or disease temporally associated with the use of a medicinal product or protocol-specified procedure, whether or not considered related to the medicinal product or protocol-specified procedure.

CTCAE term (AE description) and grade: The descriptions and grading scales found in the revised NCI Common Terminology Criteria for Adverse Events (CTCAE) version 5.0 will be utilized for AE reporting. A copy of the CTCAE version 5.0 can be downloaded from the CTEP web site (<http://ctep.cancer.gov>).

Attribution of the AE:

- Definite – The AE is clearly related to the study treatment.
- Probable – The AE is likely related to the study treatment.
- Possible – The AE may be related to the study treatment.
- Unlikely – The AE is doubtfully related to the study treatment.
- Unrelated – The AE is clearly NOT related to the study treatment.

13.1.3 Evaluating Adverse Events

An investigator who is a qualified physician will evaluate all adverse events according to the NCI Common Terminology for Adverse Events (CTCAE), version 5.0. Any adverse event which changes CTCAE grade over the course of a given episode will have each change of grade recorded on the adverse event case report forms/worksheets. All adverse events regardless of CTCAE grade must also be evaluated for seriousness.

13.1.4 Recording of Adverse Events

All adverse events will be recorded on a patient specific AE log. The AE log will be maintained by the research staff and kept in the patient's research chart. The AEs are documented in REDCAP database.

13.1.5 Reporting of AE to WCM IRB

All AEs occurring on this study will be reported to the IRB according to the IRB policy, which can be accessed via the following link:

http://researchintegrity.weill.cornell.edu/forms_and_policies/forms/Immediate_Reporting_Policy.pdf.

13.2 Definition of SAE

SAE's include death, life threatening adverse experiences, prolonged hospitalization, disability or incapacitation, overdose, congenital anomalies and any other serious events that may jeopardize the subject or require medical or surgical intervention to prevent one of the outcomes listed in this definition.

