13.2.2 Serious adverse events

Adverse events classified as serious require expeditious handling and reporting to comply with regulatory requirements. All serious adverse events, whether considered to be drug-related or not, require that a Serious Adverse Event Report Form be completed within 24 hours of the investigator becoming aware of the event. The investigator must immediately report all unexpected serious adverse events to the Institutional Review Board in writing.

Serious adverse events will be reported to:

[name]. [name] [contact] [contact]
--

14 Sub Sites:

Sub-sites participating in the trial will be given access to REDCAP e-CRFs to document adverse events based on CTCAE v5.0 in REDCAP routinely. We request that the sites complete the REDCAP baseline e-CRFs within 7 days from enrolling the patients. Adverse events have to be documented in REDCAP routinely during every follow-up visit.

Serious adverse events will be documented as per sub-site's institutional guidelines. We request sub-sites to notify [name] within 24 hours of the sub-site becoming aware of the event. Serious Adverse Events will be reported to WCMC's data safety monitoring board every 6 months.

15 Medical Monitor

This study will be monitored by the WCM Data Safety Monitoring Committee according to the procedures of the WCM Data Safety Monitoring Plan. The DSMB will be monitoring Grade 3 and above adverse events throughout the course of the study. In addition, the DSMB will also be reviewing SAE reports submitted by the study team, based on the DSMB guidelines. The WCM DSMB committee will be the medical monitor of the study.

15.1 Sub-sites:

Sub-sites will monitor the study locally and must follow sub-site's institutional guidelines. Waivers, exceptions and serious adverse events must be reported to the WCM team as and when the event occurs.

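### The SAE definition names prolonged hospitalization but not a new admission, and Section 14 does not say whether that definition binds the sub-sites

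*Combined protocol and SAP*

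**What the plan says.** Section 13.1.3 makes seriousness a separate judgement for every event: "All adverse events regardless of CTCAE grade must also be evaluated for seriousness". Section 13.2 supplies the criteria: "SAE's include death, life threatening adverse experiences, prolonged hospitalization, disability or incapacitation". It then adds overdose and congenital anomalies, and closes with a catch-all, "any other serious events that may jeopardize the subject or require medical or surgical intervention", where the intervention must serve to prevent one of the listed outcomes.

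Section 13.2.2 attaches the expedited steps to that label. SAEs, whatever their cause, "require that a Serious Adverse Event Report Form be completed within 24 hours of the investigator becoming aware of the event", and unexpected SAEs go to the IRB immediately in writing.

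For the sub-sites, Section 14 sets CTCAE v5.0 as the common standard for recording adverse events. On SAEs it says: "Serious adverse events will be documented as per sub-site's institutional guidelines". It asks sub-sites to notify a named contact "within 24 hours of the sub-site becoming aware of the event" and adds that "Serious Adverse Events will be reported to WCMC's data safety monitoring board every 6 months". Section 15.1 is firmer on reporting: "serious adverse events must be reported to the WCM team as and when the event occurs". Section 15 also has the DSMB monitor events of Grade 3 and above, and Section 15.2 sets a six-monthly review.

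**The concern.** Staff must test every adverse event against 13.2, so what the list leaves out matters. The list mentions hospitalization only in the form of a prolonged one. The study calendar (Section 9) consists of weekly assessments during radiotherapy, a visit one month after treatment and then yearly follow-up, all as clinic visits. A woman who goes into hospital during participation will usually be newly admitted, and that case is not named.

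Two things are at stake. The first is speed: the 24-hour form and the immediate IRB report start only once an event is called serious. The second is consistency. If the same admission can be classed differently by two investigators, or by the lead site and a sub-site, SAE counts partly reflect local practice. The amendment summary for version 3.0 records two added network sites, so the multi-site question is not hypothetical.

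**Working it through.** No arithmetic applies, because the plan gives no SAE or admission rate. The check sets the relevant sections side by side.

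**1. What 13.2 covers.** The phrase on hospitalization can be read as the extension of an existing stay or as a lengthy stay. Under the first reading no new admission meets it. Under the second a long new admission does and a short one does not. Under neither reading is admission itself a criterion.

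**2. What the catch-all adds.** It has two limbs.
- *Intervention needed to prevent a listed outcome.* Admission is not a listed outcome, so this limb does not make an admission serious in itself.
- *Events that may jeopardize the subject.* This limb has no such restriction and can take in an acute admission. It rests on the investigator's judgement, and it describes the events it adds as serious, so it gives no fixed test.

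Section 13.2 also introduces its list with the word *include*, so the list is not worded as closed.

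**3. How a new admission is handled as written.**

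| New admission | SAE under 13.2? | 24-hour form (13.2.2)? |
|---|---|---|
| Event also meets another listed criterion, such as life-threatening | Yes | Yes |
| Investigator judges that it may jeopardize the subject | Yes, by judgement | Yes |
| Long stay | Depends on how the phrase is read | Depends |
| Short stay, no other criterion, not judged to jeopardize | No | Not required |

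The last row is the gap. The third is an ambiguity.

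**4. Which definition the sub-sites use.** Section 14 names a shared standard for adverse events, but for SAEs it points to local guidelines for documentation. Section 15.1 has sub-sites monitor under institutional guidelines, and Section 15.4 sends them to a local monitoring board. Section 15.1 requires SAEs to be reported to the lead site but does not say whose definition decides what counts as one. No section says that 13.2 governs sub-site classification, and none says that it does not.

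**5. What limits the effect.** Adverse events are recorded whatever their cause, apart from minor laboratory abnormalities (13.1.1). The DSMB sees Grade 3 and above events whether or not they carry the SAE label (15). These provisions keep many admissions visible. They do not restore the 24-hour step, since DSMB reports are six-monthly, and they do not make SAE classification uniform.

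**The case against.** The strongest defence is that the definition is open and has a working catch-all. An investigator facing a worrying acute admission can call it serious today. Sub-sites must still report SAEs to the lead site and are asked to do so within 24 hours. The DSMB reviews Grade 3 and above events in any case, on the same six-monthly cycle, so for those events the SAE label may change little in what the board sees or when. The IRB reporting policy and the DSMB guidelines are cited but not reproduced, and they may cover initial admission. Most of this stands, and it limits the point. It does not remove it: capture through the catch-all is discretionary, and policies that are not in the documents cannot be assumed to fill the gap.

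Three stronger readings are tempting and are not supported.
- *A reader might infer that sub-sites use their own definition in place of 13.2.* Section 14 speaks of how SAEs are documented. It does not say that local guidelines replace the definition, and those guidelines are not in the documents.
- *A reader might infer that the DSMB's SAE counts already mix definitions.* The text leaves room for this but does not show that it happens.
- *A reader might infer that no new admission would ever be reported as an SAE.* The open list and the jeopardy limb rule that out.

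**Conclusion.** The point holds as a gap and an ambiguity in the wording. Followed as written, 13.2 does not require a new admission that meets no other criterion to be handled as an SAE, so the expedited steps in 13.2.2 need not start. Whether all sites classify by 13.2 is left unstated, so differences in capture between sites are a risk, not an established fact.

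The size cannot be given. If, purely as an assumption, 1% to 3% of the accrual ceiling of 430 women were admitted, that would be 430 × 0.01 = 4.3 to 430 × 0.03 = 12.9, or about 4 to 13 admissions. A reader might take this as the number of missed SAEs. It is not: the rate is not from the documents, and admissions that qualify under another criterion or the catch-all would have to be removed.

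The primary endpoint (grade 2 or higher acute toxicity) and its sample size do not use the SAE label and are unaffected. The conclusion rests on 13.2 being the operative definition and on hospital stays mostly starting as new admissions, which is inferred from the visit schedule.

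**What to change.** In Section 13.2, replace the current hospitalization item with *hospital admission or prolongation of a hospital stay*. In Section 14, state that all sites classify SAEs by Section 13.2, with local guidelines applying in addition.

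The cost is amendment wording, a memo to the sites and a few more SAE forms. No design parameter or analysis changes.
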